Appendix 22: Clinician Global Impression of Severity (CGIS)

Please choose t	he response below	that best descri	bes the severity o	of your patient's	nail psoriasis
today.					
□ None					
□ Mild					
□ Moderate					
□ Severe					
□ Very severe					

FCS Fully Conditional Specification FDA Food & Drug Administration

IA Interim Analysis

IBMCP Interim Blinding Maintenance and Communication Plan

ICH International Conference on Harmonisation

ICSR Interim Clinical Study Report

ITT Intent-to-Treat IV Intravenous

IWRS Interactive Web Response System
LOCF Last observation carried forward
MACE Major adverse cardiovascular events

MAR Missed at random

MedDRA Medical Dictionary for Regulatory Activities

MI Multiple Imputation

MMRM Mixed Model Repeated Measures

M-N Miettinen-Nurminen

mNAPSI modified Nail Psoriasis Severity Index

MNAR Missing Not at Random

NAPPA-QoL Nail Assessment in Psoriasis and Psoriatic Arthritis Quality of Life

NAPSI Nail Psoriasis Severity Index NRI Non-responder Imputation NRS Numeric Rating Scale OC Observed Cases

PASI Psoriasis Area and Severity Index

PD Protocol Deviations

PGA Physician Global Assessment

PGIC Patient Global impression of Change

PGIC-P Patient Global impression of Change for Pain

| Effective Date: 10-AUG-2020 | Page 7 of 61 |
|-----------------------------|--------------|

Sun Pharmaceutical Industries Limited

| Sun I manufectured Industries Emilied | | |
|---------------------------------------|--|--|
| PGIS | Patient Global Impression of Severity | |
| PGIS-P | Patient Global Impression of Severity for Pain | |
| PN | Preferred Name | |
| PPS | Per Protocol Set | |
| PT | Preferred Term | |
| QoL | Quality of Life | |
| SAE | Serious Adverse Event | |
| SAF | Safety Analysis Set | |
| SAP | Statistical Analysis Plan | |
| SC | Subcutaneous | |
| SD | Standard Deviation | |
| SE | Standard Error | |
| SoA | Schedule of Activities | |
| SOC | System Organ Class | |
| SPIL | Sun Pharmaceutical Industries Limited | |
| s-PGA | Static Physician's Global Assessment | |
| SSRE | Sample size re-estimation | |
| TEAE | Treatment-emergent Adverse Event | |
| ViSENPsO | Visual Medical Scale to Evaluate Nail Psoriasis Severity | |
| | | |

| Effective Date: 10-AUG-2020 | Page 8 of 61 |
|-----------------------------|--------------|

1 INTRODUCTION

This Statistical Analysis Plan (SAP) has been developed following the review of Sun Pharmaceutical Industries Limited (SPIL) Protocol TILD-18-19 (Amendment 3 dated 23 Dec 2022), and the corresponding case report form (CRF) (version 5, dated 22MAY2021). This SAP describes the analysis sets and specific details for the statistical methods to be used for the analysis and reporting of all efficacy and safety data collected during the conduct of Protocol TILD-18-19. When needed, this SAP supersedes the statistical considerations identified in Protocol TILD-18-19 and its amendments (as applicable). Where considerations are substantially different, they will be identified as such in this document. This SAP has been developed and finalized prior to database lock of the clinical database for Protocol TILD-18-19. If additional analyses are required to supplement the planned analyses or there are changes to the planned analysis described in this SAP, they may be performed and will be identified in the Clinical Study Report (CSR).

This SAP is being written with consideration of the recommendations outlined in the International Conference on Harmonisation of Technical Requirements for Registration of Pharmaceuticals for Human Use (ICH) E9 Guideline entitled "Guidance for Industry: Statistical Principles for Clinical Trials" and the most recent ICH E3 Guideline entitled, "Guidance for Industry: Structure and Content of Clinical Study Reports."

2 PROTOCOL SUMMARY

2.1 Study Design

This is a multicenter, randomized, double-blind, placebo-controlled study to assess the efficacy and safety of tildrakizumab in the treatment of moderate to severe psoriasis of the nails. Approximately 96 eligible subjects (approximately 48 per arm) with moderate to severe plaque psoriasis and concomitant moderate to severe nail psoriasis will be randomized into the study. Eligible subjects will be randomized to one of the 2 arms in a 1:1 ratio: Arm A: Tildrakizumab 100 mg, SC (n = 48) and Arm B: Placebo, SC (n = 48). The study is planned with a primary analysis, which will be performed when the last subject has completed the Week 28 visit and a final analysis to be performed when the last subject has completed the study.

The study will comprise 3 parts:

PART 1: Double-blind Placebo-controlled (Day 1 to Week 28)

After a Screening Period of up to 28 days and on Day 1, all eligible subjects will be randomized 1:1 to receive either tildrakizumab 100 mg or placebo administered by SC injection on Week 0 (Day 1), Week 4, and Week 16. Subjects should receive the first dose of study treatment within 24 hours of randomization. The treatment period for the double-blind placebo-controlled part of the study is 28 weeks.

Early Escape: At Week 16, subjects who experience significant worsening of plaque psoriasis (defined as an increase in Static Physician's Global Assessment [s-PGA] by, at least, 2 from the baseline measurement) will be eligible for early escape. Subjects selected for early escape by the Principal Investigator at Week 16 will have study medication discontinued, and will

| Effective Date: 10-AUG-2020 | Page 9 of 61 |
|-----------------------------|--------------|

complete the End of Treatment visit assessment, followed by the observational safety follow-up period. Subjects entering early escape will not be replaced for purpose of statistical analysis and will be included in the appropriate analysis populations as defined in Section 3.5.

Following the last subject's Week 28 visit (or early termination prior to Week 28), Week 28 analysis may be conducted on available data to evaluate safety and efficacy, and a Week-28 clinical study report (CSR) may be developed after database lock (DBL). In this case, when all the randomized patients have either completed the Week 28 evaluations or have stopped study participation prior to the Week 28 visit, the first database freeze (DBF) will occur (referred to as Week 28 DBF hereafter). When all patients randomized in this trial have either completed the Week 72 evaluations or have ceased study participation prior to the Week 72 visit, the second DBL will take place [referred to as the Final (Week 72) DBL henceforth], and subsequent CSR will be generated. The sponsor might opt to have a single DBL and CSR at the last subject's Week 72 visit (or early termination prior to Week 72) without a DBL at Week 28.

All assessments in PART 1 are scheduled to happen before or on the date of injection at Week 28. The analysis of efficacy and safety endpoints for PART 1 will follow the analysis visit window and definitions as specified in the sections below.

PART 2: Double-blind Active Treatment Extension (Week 28 to Week 52)

At Week 28, subjects initially randomized to placebo will be switched over to receive tildrakizumab 100 mg at Weeks 28, 32, and 44. Subjects initially randomized to tildrakizumab 100 mg will continue to receive tildrakizumab at Weeks 28, 40, and 52. In order to maintain the blind, subjects in both treatment arms will receive matching placebo injections at specified time points as described in the Schedule of Activities (SoA) in the Clinical Protocol.

Subjects who experience significant worsening of plaque psoriasis at Week 28 (defined as an increase in s-PGA by, at least, 2 from the baseline measurement) will be discontinued from treatment. Subjects who do not fulfill this criterion at Week 28 will continue to receive tildrakizumab in Part 2 as described above.

All assessments in PART 2 are scheduled to happen after the date of injection at Week 28 and before or on the date of injection at Week 52. The analysis of efficacy and safety endpoints for PART 2 will follow the analysis visit window and definitions as specified in the sections below.

PART 3: Observational Safety Follow-up (Week 52 to Week 72)

After Week 52 (or early termination of study treatment prior to Week 52), the study treatment should be stopped and all subjects, including those who terminated early from Part 1 and 2 will enter the 20-week Observational Safety Follow-up period to monitor safety and tolerability for 20 weeks following the last dose of study treatment. During the follow-up period, subjects should continue on study-approved concomitant medications only, however, may be placed on appropriate therapies for safety concerns or significant worsening of

| Effective Date: 10-AUG-2020 | Page 10 of 61 |
|-----------------------------|---------------|

psoriasis based on the judgment of the Investigator. The subjects will not receive study treatment during the follow-up period.

Subjects who withdraw from the study will undergo the assessment that corresponds to the last assessment of the study part from which they are leaving. Subjects discontinued from study treatment at any time (apart from withdrawal of informed consent) will complete the EoT (Week 52) assessment approximately 4 weeks after the last dose of study treatment and enter the 20-week Observational Safety Follow-up. Subjects who withdraw from the study during Part 3 will undergo the Week 72 (End of Study [EoS]) assessments approximately 4 weeks after their last visit.

All assessments of safety in PART 3 are scheduled to happen after the date of injection at Week 52. The analysis of efficacy and safety endpoints for PART 3 will follow the analysis visit window and definitions as specified in the sections below.

2.2 Study Objectives

The objective of this study is as follows:

2.2.1 Primary Objective

The primary efficacy objective of this study is:

To assess the efficacy of tildrakizumab in subjects with moderate to severe nail
psoriasis, as measured by the proportion of subjects who achieve at least a 75%
improvement from baseline in total-modified Nail Psoriasis Severity Index (mNAPSI)
at Week 28.

| Effective Date: 10-AUG-2020 | Page 11 of 61 |
|-----------------------------|---------------|

2.2.2 Secondary Objectives

The key secondary objective of this study is:

 To assess the efficacy of tildrakizumab in the treatment of moderate to severe nail psoriasis compared with placebo as measured by Visual Medical Scale to Evaluate Nail Psoriasis Severity (ViSENPsO) at Week 28.

The additional secondary objectives of this study are:

- To assess the effect of tildrakizumab on nail pain compared with placebo as measured by nail pain numeric rating scale (NRS) score at Week 28.
- To assess the efficacy of tildrakizumab in the treatment of moderate to severe nail psoriasis compared with placebo as measured by mNAPSI, NAPSI, and ViSENPsO at Week 28.
- To assess the efficacy of tildrakizumab in the treatment of plaque psoriasis compared with placebo, as measured by Psoriasis Area and Severity Index (PASI), Physician's Global Assessment-Skin (PGA-S) score and body surface area (BSA) involvement at Week 28
- To assess the effect of tildrakizumab on nail pain compared with placebo as measured by nail pain NRS score improvement from baseline at Week 28.

2.2.3 Other/Exploratory Objectives

The exploratory objectives of this study are:

- To assess the effect of tildrakizumab over time at measured time points through Week
 52 as measured by mNAPSI, NAPSI, Nail Pain NRS, BSA, PGA-S, static Physician's Global Assessment (s-PGA), PASI,
- To assess the effect of tildrakizumab on Quality of Life (QoL) as measured by:
 - o Dermatology Life Quality Index (DLQI) and
 - Nail Assessment in Psoriasis and Psoriatic Arthritis QoL (NAPPA- QoL).
- To assess the effect of tildrakizumab measured by using anchor scales:
 - Clinician Global Impression of Change (CGIC)
 - Clinician Global Impression of Severity (CGIS)
 - o Patient Global impression of Change (PGIC).
 - o Patient Global Impression of Severity (PGIS).
 - o Patient Global Impression of Severity for pain (PGIS-P).
 - o Patient Global Impression of Change for pain (PGIC-P).

2.2.4 Safety Objective

The safety objective of this study is:

| Effective Date: 10-AUG-2020 | Page 12 of 61 |
|-----------------------------|---------------|

 To assess the safety and tolerability of tildrakizumab in subjects with moderate to severe nail psoriasis over 52 weeks.

2.3 Study Endpoints

The study endpoint of this study is as follows:

2.3.1 Primary Endpoint

The primary endpoint of this study is:

 The proportion of subjects who achieve at least a 75% improvement from baseline in total-mNAPSI (mNAPSI75) at Week 28.

2.3.2 Secondary Endpoints

The key secondary endpoint of this study is:

 The proportion of subjects with, at least, a score of "0 - normal" or "1 - minimal nail psoriasis" and a 2-point decrease from baseline at Week 28 as measured by the ViSENPsO.

The other secondary endpoints of this study are:

- The proportion of subjects with at least 3 point decrease from baseline, in Nail Pain NRS score at Week 28 in subjects with baseline nail pain NRS score of ≥ 3 (where NRS of ≥ 3 will be based on average score from 7-daily records at Baseline.)
- Change in patient-reported nail pain NRS score from Baseline at Week 28.
- The proportion of subjects achieving total-fingernail mNAPSI 90, mNAPSI 100, NAPSI 75, NAPSI 90, and NAPSI 100 at Week 28.
- Change in total-fingernail mNAPSI score from baseline at Week 28.
- Change in total-fingernail NAPSI score from baseline at Week 28.
- The proportion of subjects achieving PASI 75, PASI 90, and PASI 100 at Week 28.
- The proportion of subjects achieving a PGA-S score of "clear" or "almost clear" with at least a 2-point reduction from baseline to Week 28.
- Percentage change in total BSA involvement from baseline to Week 28.

| Effective Date: 10-AUG-2020 | Page 13 of 61 |
|-----------------------------|---------------|

 The proportion of subjects with, at least, 30% decrease in Nail Pain NRS score from Baseline at Week 28 in subjects with a baseline nail pain NRS score of ≥ 3 (where NRS of ≥ 3 will be based on average score from 7-daily records at Baseline.)

2.3.3 Other/Exploratory Endpoints

The exploratory endpoints of this study are:

- Change from Baseline in mNAPSI, NAPSI, Nail Pain NRS, BSA, PASI, and the
 proportions of PGA-S, s-PGA, results at measured time points
 through Week 52.
- The proportion of subjects achieving a PGA-S, s-PGA score of "clear" or "almost clear" with at least a 2-point reduction from baseline through Week 52.
- Change from Baseline in DLQI score (total and 6 domain scores) and NAPPA-QoL score at measured time points through Week 52.
- The proportions of CGIC, PGIC, PGIC-P category results at measured time points through Week 52.
- Change from Baseline in CGIS, PGIS, and PGIS-P at measured time points through Week 52.
- Subjects achieving mNAPSI75, mNAPSI90 and mNAPSI100 at Week 52
- Subjects achieving NAPSI75, NAPSI90 and NAPSI100 at Week 52

[figure not shown]
2.3.4 Safety Endpoints

The safety endpoints of this study are:

- The percentage of subjects with incidence, seriousness, and severity of all adverse events.
- The percentage of subjects with severe infections, defined as any infection meeting
 the regulatory definition of a serious adverse event (SAE), or any infection requiring
 intravenous (IV) antibiotics whether or not reported as a serious event as per the
 regulatory definition.

| Effective Date: 10-AUG-2020 | Page 14 of 61 |
|-----------------------------|---------------|

- The percentage of subjects with malignancies (excluding carcinoma in situ of the cervix).
- The percentage of subjects with non-melanoma skin cancer.
- The percentage of subjects with melanoma skin cancer.
- The percentage of subjects with major adverse cardiovascular events (MACE)
- The percentage of subjects with study treatment-related hypersensitivity reactions (e.g., anaphylaxis, urticaria, angioedema, etc.).
- The percentage of subjects with injection site reactions (e.g. pain, erythema, edema etc.).
- The percentage of subjects with adverse event of clinical interest
- The percentage of subjects with abnormal physical examination findings
- Change in electrocardiogram results from baseline at Week 52
- Change from Baseline in vital signs parameters at measured time points through Week 52
- Change from Baseline in laboratory test results (Hematology, Biochemistry, and Urinalysis) at measured time points through Week 52
- Change from Baseline in C-SSRS results at measured time points through Week 52

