5.1 Inclusion Criteria

Subjects are eligible to be included in the study only if all of the following criteria apply:

- 1. Subjects should be 18 years or older at the time of signing the informed consent during the Screening visit.
- 2. Subjects with a chronic moderate to severe plaque-type psoriasis for at least 6 months (as determined by subject interview and confirmation of diagnosis through physical examination by Investigator).
- 3. Subjects must have moderate to severe nail psoriasis at Screening and Baseline, defined by:
 - mNAPSI score of ≥ 20 .
 - ViSENPsO ≥3
- 4. Subjects must have moderate to severe plaque psoriasis at Screening and Baseline, defined by:
 - s-PGA score of at least 3.
 - Body Surface Area (BSA) involvement of $\geq 10\%$.
 - PASI ≥12
- 5. Subjects must be considered candidates for systemic therapy, meaning psoriasis inadequately controlled by topical treatments (corticosteroids), and/or phototherapy, and/or previous systemic therapy.
- 6. Subjects have a negative evaluation for tuberculosis (TB) within 4 weeks before initiating study treatment, defined as a negative QuantiFERON® test. Subjects with a positive or 2 successive indeterminate QuantiFERON® tests are allowed if they have all of the following:
 - No history of active TB or symptoms of TB
 - A posteroanterior (PA) chest radiogram (with associated report available at study center) performed within 3 months of Screening with no evidence of active TB (or of any other pulmonary infectious diseases)
 - If prior latent TB infection (LTBI), must have a history of adequate prophylaxis (per local standard of care)
 - If the presence of LTBI is established, then treatment according to local country guidelines must have been followed for 4 weeks prior to inclusion in the study. A maximum of 2 QuantiFERON® tests are allowed. A re-test is only permitted if the first is indeterminate; the result of the second test will then be used.

- 7. Subjects are unlikely to conceive, as indicated by at least one "Yes" answer to the following questions:
 - Subject is a male
 - Subject is a female and agrees to abstain from heterosexual activity OR use a highly effective method of contraception as per Appendix 5.
 - Male subjects with female partners of childbearing potential who are not using birth control as described above must use a barrier method of contraception (e.g., condom) if not surgically sterile (i.e., vasectomy)

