 - Subject is a surgically sterilized female or is documented to be postmenopausal. For contraceptive guidance, see Appendix 5.
- 8. For women of childbearing potential, a negative serum pregnancy test at Screening and a negative urine pregnancy test within 24 hours prior to Day 1 and on subsequent visits at which study treatment doses are scheduled.
- 9. Subjects must have results of a physical examination within normal limits or clinically acceptable limits to the Investigator prior to Day 1. The Investigator is encouraged to consult with the Medical Monitor (or appropriate designee) if there are questions regarding the significance of any out-of-range values.
- 10. Subjects must be capable of giving signed informed consent as described in Appendix 1, which includes compliance with the requirements and restrictions listed in the ICF and this protocol.

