8.2.1 Physical Examinations

- A complete physical examination will include assessments of general appearance; skin; head/neck; pulmonary, cardiovascular, gastrointestinal, external genitourinary, lymphatic, and musculoskeletal system; extremities; eyes (inspection and vision control); nose; throat; and neurologic status.
- A detailed examination of the skin should be performed at the time points indicated in the SoA (see Section 1.3) for the efficacy assessments (e.g., ViSENPsO, NAPSI, PGA-S, PASI, BSA, etc.).
- Height and weight will also be measured and recorded at Baseline before administration of the study treatment.
- Investigators should pay special attention to clinical signs related to previous serious illnesses.

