10.3 Vital Signs

Vital signs measurements including temperature, pulse rate, systolic blood pressure, diastolic blood pressure, and respiratory rate at each scheduled visit and changes from baseline during the treatment period will be summarized by treatment arm. Vital signs will also be presented in a shift table displaying the cross tabulation of the Baseline result category versus the result of the post-treatment period at each scheduled visit. The categories of each vital sign parameters are as below:

All vital signs measurements will be listed by subject.

10.4 12-Lead Electrocardiogram (ECG)

The ECG measurements at each scheduled visit (Baseline and Week 52 Visit) and change from baseline during the treatment period will be summarized by treatment arm.

All ECG measurements and the overall interpretation will be listed by subject. Abnormal QTcF values will be flagged in the listing. QT results for subjects having no reported QTcF values will be transformed to QTcF values and flagged in the listing.

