10.5 Physical Examinations

The frequency of subjects with abnormal evaluations of body system findings for physical examinations will be summarized by visit and treatment group; abnormal physical examination findings will also be presented in a by-subject listing.

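### Physical examination safety is reported as by-visit prevalence with no Baseline comparison; a treatment-emergent count and a shift table by body system would be more informative

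*SAP*

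**What the plan says.** SAP 2.3.4 includes among the safety endpoints "The percentage of subjects with abnormal physical examination findings", with no reference state. The four endpoints listed after it (ECG, vital signs, laboratory results, C-SSRS) are all changes from Baseline, for example "Change from Baseline in vital signs parameters at measured time points through Week 52".

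SAP 10.5 puts the endpoint into practice as the frequency of subjects with "abnormal evaluations of body system findings", tabulated by visit and treatment group, plus a by-subject listing of abnormal findings. It states no shift table and no rule that separates new findings from old ones. Elsewhere in SAP section 10, laboratory data (10.2) and C-SSRS (10.6) get shift tables, vital signs (10.3) get one "displaying the cross tabulation of the Baseline result category versus the result of the post-treatment period", and ECG (10.4) gets change from Baseline.

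Protocol 9.4.2.2 first names physical examination findings together with vital signs and laboratory tests, and then promises observed values and change from Baseline. A later sentence in that section gives change from Baseline only for vital signs and laboratory tests. SAP section 1 lets the SAP override the protocol's statistical text where needed.

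On content, Protocol 8.2.1 says "A complete physical examination will include assessments of general appearance; skin; head/neck; pulmonary, cardiovascular, gastrointestinal", and the list goes on to the lymphatic system and the extremities. Protocol 5.1, criterion 4 ("Subjects must have moderate to severe plaque psoriasis at Screening and Baseline, defined by"), sets minimum s-PGA, BSA and PASI values for every subject. Criterion 9 says "Subjects must have results of a physical examination within normal limits or clinically acceptable limits to the Investigator prior to Day 1". Neither document says how psoriatic skin is to be recorded on the examination form.

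**The concern.** A safety table on examination findings should show what appeared after treatment began. Prevalence at each visit mixes three things: what was already there, what is new and what has resolved. The reader sees only the net. This holds however psoriasis is recorded.

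A second weakness is conditional. Skin is part of the examination, and skin disease is required for entry. If investigators record psoriatic skin as abnormal, the skin row starts high and falls as the skin clears, and so does any percentage pooled over systems. Part of what is filed under safety would then reflect efficacy. At stake is the readability of one descriptive safety summary, not an inferential result.

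**Working it through.** The documents give no figure for this endpoint, so there is none to reproduce.

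**1. Netting.** Take one body system and 48 subjects, the planned arm size. For illustration, 3 subjects are abnormal at Baseline and resolve, while 3 others become abnormal.
- By-visit prevalence: 3/48 = 6.3% at Baseline and 3/48 = 6.3% at follow-up, so no change is visible.
- Treatment-emergent count: 3 of the 48 − 3 = 45 subjects not abnormal at Baseline, 3/45 = 6.7%.

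**2. Dependence on how psoriasis is recorded.** None of these inputs is in the documents as such:
- r = share of subjects whose psoriatic skin is recorded as abnormal (varied from 0 to 1).
- b = share with a non-skin abnormality (10% assumed, the same at both visits).
- c = share whose skin is recorded as normal at follow-up. Values used are 2%, 30% and 62%. The outer two are the placebo and 100 mg rates of PGA clear or minimal at Week 16 in the Phase 2 study (Protocol 4.3). Minimal disease is not normal skin, so 62% is an upper bound for that visit. The 30% is an assumption.

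Pooled percentage with any abnormality:
- Baseline = 1 − (1 − r)(1 − b)
- Follow-up = 1 − (1 − r(1 − c))(1 − b)

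For r = 1, Baseline = 1 − 0 × 0.9 = 100%. At c = 62%, follow-up = 1 − 0.62 × 0.9 = 44.2%.

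| r | Baseline | c = 2% | c = 30% | c = 62% |
|---|---|---|---|---|
| 1.0 | 100% | 98.2% | 73.0% | 44.2% |
| 0.9 | 91.0% | 89.4% | 66.7% | 40.8% |
| 0.5 | 55.0% | 54.1% | 41.5% | 27.1% |
| 0.1 | 19.0% | 18.8% | 16.3% | 13.4% |
| 0 | 10.0% | 10.0% | 10.0% | 10.0% |

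The Baseline value runs from 10% to 100% according to r alone. At r = 0 there is no fall with clearance.

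**3. What pooling would hide in the extreme case.** Set r = 1 and compare two groups with assumed new non-skin findings of 2% and 10%. The pooled percentage is 1 − c(1 − new):
- c = 2%: 98.0% against 98.2%
- c = 30%: 70.6% against 73.0%
- c = 62%: 39.2% against 44.2%

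A treatment-emergent count in the non-skin systems shows 2% against 10% at every c.

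**4. Timing.** The Schedule of Activities places examinations at Screening, Baseline, Week 52 and Week 72. The placebo arm switches to tildrakizumab at Week 28 (Protocol 4.1.2). Apart from end-of-treatment examinations in subjects who stop early, every scheduled post-Baseline examination therefore comes after both arms have received active drug.

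**The case against.** A reader might infer that the endpoint starts near 100%, measures clearance rather than harm, and would not register a new lymph node or cardiac sign. The documents do not support this.

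- SAP 10.5 tabulates by body system, and Protocol 8.2.1 covers the cardiovascular and lymphatic systems. A new sign would add to its own row and appear in the listing. The masking in step 3 applies only to a pooled percentage. The wording of 2.3.4 permits one, but 10.5 does not specify one.
- Protocol Appendix 3 treats conditions newly detected after dosing, and clinically significant abnormal safety assessments, as adverse events. It leaves out expected signs of the disease under study. The adverse event tables therefore already carry most of the clinically important information.
- The 100% figure requires r = 1. The documents do not fix r, criterion 9 accepts results that are clinically acceptable, and psoriasis severity is scored separately.
- Given the timing in step 4, any drift is mainly a before-after change, not a distortion of the placebo comparison.
- SAP section 16, the list of tables, and the table mock-ups are not in the text available, so a shift table might be planned there. Protocol 9.4.2.2 also points towards a change from Baseline.

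All of this limits the harm. It does not supply a Baseline comparison in SAP 2.3.4 or 10.5. The protocol's later sentence and the SAP's precedence mean that 9.4.2.2 cannot be relied on to fill the gap.

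**Conclusion.** The point holds as a minor improvement. Of the five non-AE safety domains in SAP 2.3.4, physical examination is the only one for which the SAP text states no Baseline comparison. Net prevalence can hide new findings behind resolved ones (6.3% at both visits in the example). That conclusion needs no assumption about recording.

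The link to psoriasis clearance is conditional: from no effect at r = 0 to a fall from 100% to 44.2% at r = 1, b = 10% and c = 62%. It concerns the skin row or a pooled percentage, not the other body-system rows. Alpha, power and the efficacy conclusions are unaffected.

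**What to change.** In SAP 2.3.4 and 10.5, define the endpoint as the percentage of subjects with a treatment-emergent abnormal finding (not abnormal at Baseline, abnormal post-Baseline) by body system. State the denominator. Show skin as its own row and do not pool it with other systems. Add a normal/abnormal shift table from Baseline to Week 52 (EoT) and Week 72, and keep the by-subject listing.

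Excluding psoriatic findings or grading findings as worsened is not proposed, because either would need CRF fields that the documents do not show. One limit remains: a subject whose skin is already abnormal at Baseline cannot become a new case in the skin row, so new skin findings there still rest on the listing and the adverse event data.

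The cost is revised wording and one extra descriptive table from normal/abnormal results already recorded.
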